6.8 Follow-Up after 6 Months (Visit 6)

The following evaluations will be performed at Visit 6, which are described in details in Section 7:

- Oral hygiene assessment
- Plaque Index (PI)
- mSBI
- Probing Pocket Depth (PPD)
- · Photograph of the implant site
- Implant success criteria
- Implant survival
- PES
- AEs
- Changes in concomitant medications

6.9 Follow-Up after 12 Months (Visit 7)

The following evaluations will be performed at Visit 7, which are described in details in Section 7:

- Oral hygiene assessment
- PI
- mSBI
- PPD
- Photograph of the implant site
- X-ray
- Implant success criteria
- Implant survival
- PES
- AEs
- Changes in concomitant medications

7 Study Evaluations

7.1 Informed Consent

It is the responsibility of the Investigator, or an authorized person designated by the Investigator to obtain informed consent in writing from each patient participating in this study prior to any study related procedures. As part of the informed consent discussion, the Investigator must provide an adequate explanation of the overall requirements/procedures of the study, purpose of the study, the nature of the planned treatment, any alternative procedures, and possible risks, complications, or benefits of the study. The Investigator or designee must also explain that the patients are completely free to refuse to enter the study or to withdraw from the study at any time for any reason without prejudice. Ample time must be provided for the patient to read and understand the Informed Consent Form and to consider participation in the clinical investigation. Patients must read, understand and sign the written patient information sheet. The consent form must be personally signed and dated by the patient and the person obtaining consent. Investigators should keep the original signed informed consent document in a secure location. A copy of the signed consent form should be given to the patient. The electronic Case Report Form (eCRF) for this study contains a section for documenting informed consent, and this must be completed appropriately.

The informed consent must be approved by an Ethics Committee (EC) before consenting can begin. The Informed Consent Form must be available in the primary language of the patient. It is written in accordance with the "Declaration of Helsinki" (as adopted by the 18th World Medical Assembly, 1964, and as revised in Tokyo (1975), Venice (1983), Hong Kong (1989), Somerset West (1996), Edinburgh (2000), Seoul (2008), and Fortaleza (2013) (WMA General Assembly, 2013)) and applicable local regulations.

If new safety information results in significant changes in the risk/benefit assessment, the consent form will be reviewed and updated if necessary. All enrolled patients should be informed of the new information and be given a copy of the revised form. The patients must give their consent to continue the study, unless the patient was considered a screening failure (see Section 11.3.4).

7.2 Pregnancy Test

Women of child-bearing potential (women who are not surgically sterile or postmenopausal (defined as amenorrhea for >12 months)) must perform a pregnancy test (validated over-the-counter test) at Visit 1, before the study required radiographs are taken, to confirm that the woman is not pregnant. The test result must be documented in the source data. A woman who

is pregnant or planning to become pregnant at any point during the study duration cannot be enrolled in this study.

If a woman becomes pregnant during the study, an AE form should be completed. The woman should be followed for the duration of the pregnancy, without the study required peri-apical radiographs, and the outcome of the pregnancy should be documented (Section 8.5).

7.3 Demographics

Patient demographics (date of birth, gender and ethnic origin) need to be documented at screening (Table 2).

7.4 Smoking Status

Smoking status need to be documented at screening (Table 2). It will be assessed if patients are current or past smokers and they will be classified into:

- Non-smokers
- Light smokers: 1 to ≤ 10 cigarettes per day
- Heavy smokers: > 10 cigarettes per day

7.5 Inclusion and Exclusion Criteria

At screening, the inclusion and exclusion criteria will be evaluated according to Sections 3.7.1 and 3.7.2, and will be re-evaluated at baseline. Patients must fulfill all of the inclusion criteria and must not meet any of the exclusion criteria to be eligible for enrollment in the study.

7.6 Medical and Dental History / Pre-Operative Planning

Medical and dental history / pre-operative planning will be obtained at the Screening Visit (Table 2). Relevant medical history (e.g., systemic diseases) and current medical conditions will be evaluated by the Investigator based on the information available. The information may be obtained from the patient's general physician or from oral communication with the patient. Dental history / pre-operative planning should include position of the missing tooth, description of tooth loss, description of the adjacent dentition, prosthetic history and details of bone augmentation procedures if applicable.

7.7 Oral Hygiene Assessment

The patient's overall oral hygiene will be evaluated at each study visit (Table 2) starting with the Screening Visit by choosing one of the following: "excellent", "good", "fair" or "poor".

7.8 Plaque Index

Plaque Index will be assessed at the time points listed in the schedule of assessment (Table 2).

It will be evaluated on the mesial, buccal, distal and palatal surfaces of the implant site using the four-point scale PI developed by Silness and Loe (Silness and Loe 1964):

- Score 0 no plaque.
- Score 1 a film of plaque adhering to the free gingival margin and adjacent area of the tooth. The plaque may be seen in situ only after application of disclosing solution or by using the probe on the tooth surface.
- Score 2 moderate accumulation of soft deposits within the gingival pocket, or the tooth and gingival margin which can be seen with the naked eye.
- Score 3 abundance of soft matter within the gingival pocket and/or on the tooth and gingival margin.

7.9 Modified Sulcus Bleeding Index

Modified Sulcus Bleeding Index will be assessed at the time points listed in the schedule of assessment (Table 2).

It will be documented if bleeding is induced at the marginal gingival tissue by running a blunt periodontal probe along the soft tissue wall at the orifice of the pocket. The bleeding tendency will be evaluated on the implant site at 4 locations (mesial, buccal, distal, palatal) and assessed using the mSBI by Mombelli (Mombelli et al. 1987):

- Score 0 no bleeding when a periodontal probe is passed along the gingival margin.
- Score 1 isolated bleeding spot visible.
- Score 2 blood forms a confluent red line on margin.
- Score 3 heavy or profuse bleeding.

7.10 Probing Pocket Depth

Probing Pocket Depth will be assessed at the time points listed in the schedule of assessment (Table 2).

The PPD will be measured at the implant site by recording the distance in millimeters from the gingival margin to the bottom of the probable pocket at 4 locations (mesial, buccal, distal, palatal).

7.11 Photograph of the implant site

Digital intra-oral photographs should be taken at each study visit (Table 2):

- Visit 1
- Visit 2:
 - After surgical flap
 - After implant bed preparation
 - After implant insertion (photograph should include augmentation, if applicable)
 - When surgery is completed
- Visit 3
- Visit 4:
 - Before re-opening
 - After re-opening
- Visit 5:
 - Before insertion of the final crown (after the provisional one was removed)
 - After insertion of the final crown
- Visit 6
- Visit 7

7.12 Panoramic Radiograph or Cone-Beam Computed Tomography Scan

A panoramic radiograph or full mouth CBCT scan must be available at the Screening Visit to assess the complete dentition and to use in surgical planning. The screening panoramic radiograph or full mouth CBCT scan can be taken during the Screening Visit or be available from a previous date within 6 months of the implant surgery (Table 2).

7.12.1 Bone Level Changes

Peri-apical X-rays are standard procedures during implant surgery to assess changes of the bone level. Peri-apical X-rays will be taken at baseline (Visit 2), at placement of the final crown (Visit 5) and at the end of the study (Visit 7) to assess bone level changes between implant placement (Baseline Visit) and placement of the final crown (Visit 5) as well as between implant placement and the 12-month Follow-Up Visit (Visit 7) (Table 2).

An independent expert will be contracted to perform the bone level measurements from the X-rays. The vertical bone level will be evaluated by measuring the distance from the implant shoulder to the first visible bone contact on the implant. Measurements will be taken at the mesial and distal aspects of the implant, and an average value will be calculated. Mean bone level changes will be computed by subtracting the average bone level at Visit 5 from the average bone level at baseline (implant placement) and by subtracting the average bone level at the 12-month Follow-Up Visit (Visit 7) from the average bone level at baseline (implant placement). Hence, negative bone level changes are representing bone loss between baseline and Visit 5 and between baseline and the 12-month Follow-Up Visit, respectively; vice versa positive changes representing bone gain. Measurements will take into account distortion based on changes on the radiograph from the true dimension of the implant.

7.13 Implant Success Criteria

Implant success will be assessed at the time points listed in the schedule of assessment (Table 2).

A "successful implant" is an implant where all of the following success criteria (according to Buser et al., 1990) apply:

- Absence of persisting subjective discomfort such as pain, foreign body perception and/or dysesthesia (painful sensation);
- 2. Absence of recurrent peri-implant infection with suppuration;
- Absence of tactile implant mobility;
- 4. Absence of a continuous peri-implant radiolucency.

Failed implants will be counted as not successful.

7.14 Implant Survival

Implant survival will be assessed at the time points listed in the schedule of assessment (Table 2).

A "surviving implant" is an implant stably inserted in the jaw. Note, that a surviving implant may not be successful if the success criteria (see Section 7.13) are not fulfilled.

A "failed implant" is an implant that:

- Has been removed; or
- Has fractured beyond repair.

[figure not shown]

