3.4 Endpoints

3.4.1 Primary Endpoint

The following parameter will be measured as primary endpoint:

• Implant survival at 12 months after implant placement

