8.2.4 Expectedness

If the AE is judged to be related to the study device or procedure, i.e., is an ADE, the Investigator will make an assessment of expectedness, or anticipation, based on knowledge of the reaction and any relevant product information as documented in the IfU (Annex 1) or in the

list of potential expected ADEs in the current protocol (Table 6) following the insertion of dental implants. The event will be classed as either:

- Expected the reaction is consistent with the effects of the device listed in the IfU
 (Annex 1) or list of potential expected ADEs in the current protocol (Table 6) following the insertion of dental implants.
- Unexpected the reaction is not consistent with the effects listed in the IfU (Annex 1) or list of potential expected ADEs in the current protocol (Table 6) following the insertion of dental implants.

Table 6: List of Potential Expected Adverse Device Effects Following the Insertion of Dental Implants

Biological complications

Peri-implant mucositis

- Bleeding (bleeding on probing)
- Bruising
- Mucosal/gingival inflammation (=gingivitis/mucositis, inflammation of the gum tissue)/redness
- Gingival enlargement (=gingival hyperplasia, gingival hypertrophy, gum overgrowth, hypertrophic gingivitis)
- Gingival recession (=dehiscence of the gingiva, receding gums)
- Pain (discomfort)
- Suppuration
- Swelling

Peri-implantitis

- Bleeding (bleeding on probing)
- Bone loss around implant (=peri-implant bone loss)
- Bruising
- Infection at implant site without suppuration
- Infection at implant site with suppuration (=peri-implant abscess)
- Systemic infection
- Pain
- Swelling

Bone integration deficiency

- No primary stability (at surgery)
- Implant mobility (tactile horizontal or vertical)
- Early loss/failure of implant (i.e. before osseointegration) (=primary implant failure)
- Late loss/failure of implant (i.e. after osseointegration) (=secondary implant failure)
- Radiolucency
- Aspiration of implant
- Swallowing of implant

Non-plaque related

- Foreign body sensation
- Material allergy
- Oro-sinus or oro-nasal intrusion/fistula
- Permanent paresthesia/dysesthesia
- Temporary or permanent nerve damage in the jaw

Mechanical complications

- Loosening of abutment or prosthetic screw
- Loosening of an healing cap
- Loss/failure of an abutment
- Loss/failure of an healing cap
- Fracture of abutment or prosthetic screw
- Fracture of implant

Technical complications

- · Fracture of prosthesis or veneer

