11.3.5 Early Withdrawal

Any patient may withdraw from the study any time without prejudice and will be offered an alternative treatment related to their dental condition. Patients will be advised of the need for the prescribed follow-up visits for their ongoing care and well-being.

The Investigator may withdraw any patient from the study in the case of:

- Non-compliance with the protocol
- Failure to attend the follow-up visits
- SAE or AE, which in the opinion of the Investigator prevents the patient's further participation in the study.

The Investigator must withdraw any patient from the study in the case of:

Implant loss

The patient withdrawal will be documented on a Study Termination eCRF page and must include the reason for the patient withdrawal. Withdrawn patients will not be replaced and cannot be re-enrolled.

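### Does Section 7.14 leave the 12-month survival status of a mobile implant still in place undecided?

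*Combined protocol and SAP*

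**What the plan says.** The primary endpoint in Section 3.4.1 is "Implant survival at 12 months after implant placement". Section 7.14 defines two terms. A surviving implant "is an implant stably inserted in the jaw". A failed implant is one that meets either of two conditions, the first being "Has been removed; or" and the second a fracture that cannot be repaired. A note in the same section adds that "a surviving implant may not be successful if the success criteria" of Section 7.13 are not met. Section 7.13 has four criteria: no persisting discomfort, no recurrent infection with suppuration, "Absence of tactile implant mobility", and no continuous radiolucency. It also counts failed implants as unsuccessful.

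A third term, implant loss, appears elsewhere. Table 6 in Section 8.2.4, the list of expected adverse device effects, includes "Late loss/failure of implant (i.e. after osseointegration) (=secondary implant failure") and, as a separate item, "Implant mobility (tactile horizontal or vertical"). Section 11.3.5 states "The Investigator must withdraw any patient from the study in the case of" one event, implant loss.

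Section 9.1.2 makes the full analysis set (FAS) the basis of the primary analysis and keeps patients who stopped early. Section 9.1.3 limits the per-protocol set (PPS) to patients who completed Visits 1 to 7 with the primary variable available, and gives it a supportive role. Section 9 describes the study as descriptive.

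**The concern.** Surviving and failed are not written as complements. An implant in place but mobile at Visit 7 is neither removed nor fractured, so it is not failed. Whether it survives depends on what stable means, and Section 7.14 names no test for that at follow-up. Because mobility is one of the success criteria, the note could be read to mean that such an implant survives but is not successful. Two analysts could then report different primary results from the same data.

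The PPS seemed most at risk. If implant loss in Section 11.3.5 covers every lost, removed or irreparably fractured implant, patients with those events before Visit 7 are withdrawn and cannot be in the PPS. Apart from failures first found at Visit 7, only mobile implants could then lower PPS survival. If they count as surviving, the PPS figure is 100% however many implants were lost earlier.

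**Working it through.** **The wording.** The outcome to be reported is survival, so the question for each implant is whether it meets the definition of surviving.

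| State of the implant at 12 months | Meets the surviving definition? | On the failed list? |
|---|---|---|
| In place and stable | Yes | No |
| Removed, or lost from the jaw | No | Yes if removed; a spontaneous loss is not named |
| In place, fractured beyond repair | Counted as failed | Yes |
| In place and mobile | No, on the plain words | No |

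The last row lacks a failed label, but the endpoint does not need one. Survival is settled by the second column. Success is settled too, since a mobile implant misses a criterion in Section 7.13.

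The note does not overturn this. It says that an implant already classed as surviving can still be unsuccessful. The discomfort, infection and radiolucency criteria, three of the four, give that statement content with no mobile implant involved. Nowhere does it say that a mobile implant survives.

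**The size.** The plan states no survival rate, precision target or mobility rate, so there is no figure of its own to reproduce. Inputs:

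- n = 40, the minimum enrolment in Section 3.5, with one assessed implant per patient (Section 3.3).
- M = 1 implant in place and mobile at Visit 7 (assumption).
- L = 0 to 3 implants lost, with withdrawal, before Visit 7 (assumption).
- No other missing data, all 40 patients in the FAS, and no other PPS exclusions (assumption).

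Formulas, with the mobile implant counted as not surviving or as surviving:

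- FAS: (40 − L − M)/40 or (40 − L)/40
- PPS: (40 − L − M)/(40 − L) or (40 − L)/(40 − L)

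| L | FAS, not surviving | FAS, surviving | PPS, not surviving | PPS, surviving |
|---|---|---|---|---|
| 0 | 39/40 = 97.5% | 40/40 = 100% | 39/40 = 97.5% | 40/40 = 100% |
| 1 | 38/40 = 95.0% | 39/40 = 97.5% | 38/39 = 97.4% | 39/39 = 100% |
| 2 | 37/40 = 92.5% | 38/40 = 95.0% | 37/38 = 97.4% | 38/38 = 100% |
| 3 | 36/40 = 90.0% | 37/40 = 92.5% | 36/37 = 97.3% | 37/37 = 100% |

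Across a row, the two readings differ by 2.5 points in the FAS and by 2.5 to 2.7 points in the PPS, so the ambiguity is no larger in the PPS in any way that matters. For scale, the exact (Clopper-Pearson) 95% interval is 91.2 to 100% for 40/40 and 86.8 to 99.9% for 39/40. The shift is small beside the sampling uncertainty.

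Down a column, three early losses lower FAS survival by 7.5 points on either reading. PPS survival falls by 0.2 points on one reading and not at all on the other. The PPS therefore misses early losses on both readings. The cause is mandatory withdrawal (Section 11.3.5) combined with the completion condition (Section 9.1.3). Rewording Section 7.14 would not bring those patients back.

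**The case for a change.** The strongest reply is that stable is tested by hand only at placement (Sections 6.3 and 7.18) and is not defined for follow-up. Five centers score survival themselves; the independent expert in Section 7.12.1 measures bone level only. One implant decides whether the report says 100%, and the event need not be rare. The chance of at least one mobile implant among 40 is 1 − (1 − p)^40, which gives 33%, 55%, 70% and 87% at assumed rates p of 1%, 2%, 3% and 5%. A short added sentence would cost little and would prevent a choice made after the data are seen.

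Part of this stands. Section 7.14 is not exhaustive, it does not say how stability is judged at follow-up, and implant loss is not tied to its terms. But the plain reading gives an answer, and an analyst who follows it gets a sound result. Tactile mobility is part of the Visit 7 examination (Sections 6.9 and 7.13) and is also a listed adverse device effect, so a reader can recover the other figure if the mobile implants are counted in the report. The term implant loss does no harm to the FAS: a lost implant is not stable in the jaw, and Section 9.1.2 keeps the withdrawn patient. Table 6 is a safety list and does not define the endpoint.

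**Conclusion.** The definitions in Section 7.14 are incomplete in form, but the primary endpoint can be scored from them. An implant in place but not stable at Visit 7 is not surviving, even though it is not listed as failed. This is a gap that analysts fill sensibly, and no change to the plan follows from it.

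The amount at issue is 2.5 points of survival per mobile implant at n = 40, and nothing if there is none. It bears on no test, margin or decision. The conclusion rests on reading stable in its ordinary sense, and on the Visit 7 data showing which implants were mobile; the eCRF itself is not in the documents. The insensitivity of the PPS to early losses is real, but it belongs to Sections 11.3.5 and 9.1.3 and is the same problem whichever way Section 7.14 is read. The FAS, which carries the primary analysis, does register those losses.

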7.15 Pink Esthetic Score

PES will be assessed by the Investigator at the time points listed in the schedule of assessment (Table 2). The PES score allows an objective evaluation of peri-implant soft tissue of single tooth implants based on 7 parameters (Table 4 and Figure 1) and is highly reproducible. Each variable will be assessed using a 0-1-2 scoring system; 0 being the lowest, and 2 being the highest value. The maximum achievable PES is 14 (Fürhauser et al., 2005).

Table 4: Pink Esthetic Score Variables

	Score				
Variablen	0	1	2		
Variables					
(1) mesiale Papille	fehlt	unvollständig	vollständig		
(1) mesial papilla	missing	incomplete	complete		
(2) distale Papille	fehlt	unvollständig	vollständig		
(2) distal papilla	missing	incomplete	complete		
(3) Weichgewebe-Kontur	unnatürlich	fast natürlich	natürlich		
(3) soft tissue contours	unnatural	virtually natural	natural		
(4) Weichgewebe-Level	Diskrepanz > 2 mm	Diskrepanz 1-2mm	Diskrepanz < 1 mm		
(4) soft tissue level	discrepancy > 2 mm	discrepancy 1–2mm	discrepancy < 1 mm		
(5) Alveolarfortsatz	deutlich vermindert	leicht vermindert	Kein Unterschied		
(5) aleveolar process	clearly resorbed	slightly resorbed	no difference		
(6) Weichgewebe-Farbe	deutlicher Unterschied	leichter Unterschied	kein Unterschied		
(6) soft tissue coloring	clear difference	slight difference	no difference		
(7) Weichgewebe-Textur	deutlicher Unterschied	leichter Unterschied	kein Unterschied		
(7) soft tissue texture	clear difference	slight difference	no difference		

Figure 1: Visualization of the Pink Esthetic Score Variables

Refer to Table 4 for description of the variables.

7.16 Adverse Events

At each visit the Investigator should determine if any AEs occurred since the last study visit by speaking with the patient and reviewing any dental and medical records. These AEs, along with any AEs from the current study visit, should be documented and reported as described in Section 8 of the protocol. In addition the Investigator should evaluate the status of any ongoing AEs throughout the study as specified in Section 8.4.

7.17 Concomitant Medication

Concomitant medication, procedures and supportive therapies will be recorded at the Screening Visit. Any changes in the concomitant medications, procedures and supportive therapies must be documented at each study visit until the end of the study. Prophylactic antibiotics and anesthesia given do not need to be recorded on the Concomitant Medication eCRF page as long as they are taken by the patients in the same or lower dosage as during standard treatment during the following procedures:

- Visit 2: Implant placement
- Visit 3: Suture removal
- Visit 4: Placing of the provisional crown
- Visit 5: Placing of the final crown.

